The FDA has reviewed the study and gave an FDA IND (#145,538). Approved was also given by the research divisions of Cumberland Pharmaceuticals (Cumberland Pharmaceuticals have agreed to donate N-acetylcysteine for the study).

10) Study Design

1) The treating ED physicians (other than the investigator or coinvestigators) will identify potential subjects in the Emergency Department at Harbor UCLA via initial evaluation (standard of care) including blood draw for a standard CVA panel (CBC, Chemistries, PT, PTT, neuronal specific enolase, s100b) and brain imaging. Subjects who present with neurological deficits consistent with stroke without hemorrhage less than 24 hours since symptom onset will be asked to whether they would be interested in participation in a research in our study and if so, the treating ED physician will contact investigators or study team member. Investigators or study team member may access medical record to confirm eligibility before approach subject.

If treating physician is member a co-investigator/ study team member, s/he will approach subject about participation once deemed to meet eligibility criteria. (See inclusion and exclusion criteria below). Informed consent will be obtained for all subjects either from the subjects themselves or if they do not have capacity, from their legally authorized representative (See Section 16 below).

2) Each subject will undergo, as part of standard of care, evaluation and assessment using the National Institutes of Health Stroke Scale (NIHSS) and the Modified Rankin Scale (MRS) which have been similarly used in the European Cooperative Acute Stroke Study III, ECASS III (3). The NIHSS is a 15-item scale that measures the level of neurologic impairment. The MRS is a measure of disability with scores ranging from 0 (no symptoms at all) to 6 (death). Individuals must have an NIHSS of at least 5 to be eligible for this study. This data will be recorded for study purposes using a standard data collection sheet.

3) Subjects will receive standard of care with the study intervention being considered an “add-on” therapy. Thirty minutes after enrollment, eligible subjects will be randomized into one of two arms: placebo or NAC.

PROTOCOL TITLE: Randomized Placebo Controlled Trial of Intravenous N-Acetylcysteine for the Treatment of Acute Ischemic Stroke

Any patient receiving t-PA who enrolls in the study will have their study drug infusion delayed by 24 hours after the completion of the t-PA infusion.

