4) Subjects will be contacted by telephone 24 hours post discharge, 3 days post discharge, and at 7 days to be monitored for adverse events and asked whether they have had any new symptoms or problems since the last study assessment. This will be an open question that will be recorded prospectively for each subject. If the subject reports an adverse event this is still present at the time of the phone call and wants to be further evaluated, they will be told to return to the emergency department and seen by a physician not associated with the investigation. Further the investigator from

PROTOCOL TITLE: Randomized Placebo Controlled Trial of Intravenous N-Acetylcysteine for the Treatment of Acute Ischemic Stroke

the team will also meet them in the Emergency Department to detail the information. All adverse events, whether they are deemed mild or serious, will be forwarded immediately to the Medical Monitor who will have discretion on whether to halt the study or continue. The Medical Monitor's reports will be forwarded to the Institutional Review Board (IRB). In addition, all unanticipated problems pose a risk to subjects or others will be reported to the Institutional Review Board (IRB) as required by FDA regulations. (There is no sponsor for this study, so no report needs to go to a sponsor).

4) Subjects will be instructed to return to the neurology clinic on day 30 and day 90 for re-evaluation. The same assessment will be performed as on day zero: the NIHSS and the MRS as well as the Glasgow Outcome Scale (GOS) and Barthel Index (BI). The GOS is a 5-point scale on which 5 indicates independence and 1 death. The BI assesses the ability to perform activities of daily living, on a scale that ranges from 0 (complete dependence on help with activities of daily living) to 100 (independence). These scores will be recorded on a standard data collection sheet. A representative from the neurology department will perform the examination, blinded from the previous scoring and treatment. In addition to the neurologic evaluation, patients will be queried at this time as to whether they experienced any nausea, vomiting, flushing, and itchiness, wheezing or difficulty breathing between the time of their discharge and the reevaluation.

For convenience, the 30 day follow up will have a tolerance range +/- 3 days and the 90 day follow up will permit +/- 10 day window.

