First, subjects will be screened for neurological deficits consistent with cerebral vascular accident via history, physical examination and emergent evaluation in the Emergency Department which will include a noncontrast CT of the brain and an emergent Stroke Code, where our Neurology team will immediately consult on the patient at the bedside.

As part of the initial evaluation, the patient will be assessed with the National Institutes of Health Stroke Scale (NIHSS) which uses a 15-item scoring system to assess the level of neurological impairment. The items assessed include: Level of consciousness (LOC) responsiveness, LOC questions, LOC commands, best gaze, visual field, facial palsy, best motor arm, best motor leg, limb ataxia, sensory function, neglect, dysarthria, best language, extinction and inattention, formerly called neglect (31, 32).

PROTOCOL TITLE: Randomized Placebo Controlled Trial of Intravenous N-Acetylcysteine for the Treatment of Acute Ischemic Stroke

A Modified Rankin Scale (MRS) will also be obtained; The MRS is a simple scoring system that runs from 0-6, from perfect health without symptoms to death. 1- no significant disability, able to carry out all usual activities, despite some symptoms. 2 - slight disability, able to look after own affairs without assistance, but unable to carry out all previous activities. 3 - moderate disability, requires some help, but able to walk unassisted. 4 - moderately severe disability, unable to attend to own bodily needs without assistance, and unable to walk unassisted. 5 - severe disability, requires constant nursing care and attention, bedridden, incontinent.

The neurology consult team in conjunction with the Emergency Department will then make an assessment as to whether the patient is eligible to receive treatment with t-PA (based on national criteria of the American Heart Association and American Stroke Association - https://www.stroke.org/-/media/Stroke-Files/Ischemic-StrokeProfessional-Materials/AIS-Toolkit/AIS-Professional-EducationPresentation-ucm_485538)

NAC or placebo infusion will be started 30 minutes after the enrollment of the study. For subjects who receive t-PA, NAC or placebo infusion will be started 24 hours after the conclusion of the t-PA infusion.

Prior to the starting of the study medication, all subjects will receive 12.5 mg intravenous diphenhydramine to reduce the incidence of allergic reactions.

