All subjects would then be admitted to the Neurology Service to either an Intensive Care Unit bed or a Step-down intensive care unit bed.

Subjects will return to neurology clinic on days 30 and 90 and undergo reevaluation by a neurology resident using the same assessments performed on day 0. Data will be collected on a standard data collection sheet at each visit. In addition, the subjects will undergo the following two assessments:

Glasgow Outcome Scale (GOS, follow-up visits only):

GOS is a 5-point scale on which 1- death, 2- persistent vegetative state, 3- severe disability, 4- moderate disability, and 5- low disability.

Barthel Index (BI, follow-up visits only):

BI evaluates the ability to perform activities of daily living, on a scale that ranges from 0 to 100. Activities assessed include: presence or absence of fecal incontinence, presence or absence of urinary incontinence, help needed with grooming, with toilet use, with feeding, with transfers, with walking, with dressing, with climbing stairs, and with bathing.

These follow-up visits are standard of care. These tests are standard physical assessments done by the neurologists, and no specific interventions will be made for the study. Our study team will review EMR to obtain results/notes.

5. Each patient will complete two separate MRI's of the brain, which are both standard of care. The MRI's are considered standard of care and will not be different in acquisition than MRI's currently obtained for stroke patients. We will use software packages available to post-process these images for research purposes as outlined in the protocol.

6. Patients will have a "stroke panel" of lab tests as mentioned above, which are the standard of care at our facility. The total amount of blood obtained for the entire duration of the study will be less than 100ml.

7. We will also pre-define a per-protocol (excluding Stroke Mimics as defined as a negative brain MRI obtained within 2 weeks of the onset of symptoms) versus an intent to treat protocol. This would allow for the loss of study subjects who might stop the NAC after a negative MRI who are no longer thought to have had a Stroke.

g) Data and Specimen Banking

No specimens will be stored.

Data Collection sheets will be utilized for initial assessment and follow up. See attached documents.

h) Data Management

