All subjects will be monitored closely by hospital staff either in the Emergency Department or the hospital's monitored units (Intensive Care Unit or Step Down Unit) with vital signs obtained every 15 minutes, and neurologic symptom checks completed every hour. The staff will be trained to observe for common side effects of the NAC infusion which may include nausea, vomiting, flushing, and pruritus along with the more uncommonly seen wheezing and bronchospasm or rarely angioedema and hypotension. Investigators will also prospectively ask the subjects every four hours to report if they are or have experienced any nausea, vomiting, flushing, itchiness or experienced wheezing or had any trouble breathing. Investigators will also prospectively monitor/record vital signs every 15 minutes for the first 4 hours after the NAC administration and look for evidence of anaphylactoid reactions or other allergic reactions. If any of the uncommon or rare drug effects are detected by nursing or by the investigators, there will be standing orders to stop the NAC infusion and immediately contact the physician caring for the patient. If a mild symptom occurs, the staff will be informed to contact the treating physician to assess the patient. For serious adverse events (defined by the discretion of the treating physician), the NAC will be unblinded and the information given to the treating physician and the medical monitor. At the same intervals, subjects will also be queried as to whether they have had any new symptoms or problems since the last study assessment to obtain data on a broader range of possible adverse and serious adverse events that may be unexpected or not typically associated with NAC infusions. All adverse events will be immediately reported to the Medical Monitor who will have the authority to immediately halt the study pending further review by the Lundquist Institute's IRB and the FDA.

In addition, subjects will be contacted by telephone 24 hours post discharge, 3 days poste discharge, and at 7 days to be monitored for adverse events and asked whether they have had any new symptoms or problems since the last study

PROTOCOL TITLE: Randomized Placebo Controlled Trial of Intravenous N-Acetylcysteine for the Treatment of Acute Ischemic Stroke

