assessment. This will be an open-ended question that will be recorded prospectively for each subject. If the subject reports an adverse event this is still present at the time of the phone call and wants to be further evaluated, they will be asked to return to the emergency department and seen by a physician not associated with the investigation. Further the investigator from the team will also meet them in the Emergency Department to detail the information. All adverse events, whether they are deemed mild or serious, will be forwarded immediately to the Medical Monitor who can immediately halt or terminate the study. In addition, all adverse events will be reported to the IRB of the Lundquist Institute by the investigators (and independently by the Medical Monitor). In a written IND safety report, any adverse experience associated with the use of the drug that was both serious and unexpected will be immediately reported to the FDA.

Definition of adverse events for this protocol:

Adverse Events

Symptoms that are new or unexpected reported by the subject

Nausea, diaphoresis, chest pain, abdominal pain, paresthesias, headache, visual complaints

Cough, pruritis, rash

Laboratory abnormality

Minor bleeding from gums, nares

Mild Sedation

Serious Adverse Events

Significant adverse events that led to an intervention, including withdrawal or dose reduction in the investigation drug or the need for concomitant therapy

Wheezing, bronchospasm, angioedema requiring rescue medications

Bleeding requiring an intervention

Hemorrhagic conversion of the ischemic CVA

Worsening neurologic condition as measured by the NIHSS at 4 hour intervals after enrollment in the study (or sooner as dictated by the care of the neurology team)

Laboratory abnormality requiring intervention (e.g. severe hyponatremia or hyperkalemia)

Death

k) Withdrawal of Subjects

Subjects will be withdrawn if they leave AMA/elope during their initial hospitalization or do not complete their 30 day or 90 day follow up prior to completion of the study

11) Risks to Subjects

Risk of N-Acetylcysteine:

Most adverse drug reactions that have been reported are minor and easily managed. Serious anaphylactoid reactions are extremely rare (11, 33-36)

Common: Nausea, vomiting, flushing, and pruritus,

Uncommon: Wheeze and bronchospasm (7.1%) Rare:

Angioedema, and hypotension (25-28)

Risks of Diphenhydramine

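### Every event classed as serious unblinds the treating physician, whether or not care requires it, and nothing protects the day-90 rater's blinding after a code break

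*Combined protocol and SAP*

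**What the plan says.** **Trigger and recipients.** Section 10(j), under the tracking of adverse events, covers serious events as follows: "defined by the discretion of the treating physician), the NAC will be unblinded and the information given to the treating physician". The medical monitor receives the assignment too. The physician's discretion concerns what counts as serious. Once an event is so classed, disclosure follows.

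**A second definition.** Later in Section 10(j) a fixed list of serious adverse events appears. It includes "Worsening neurologic condition as measured by the NIHSS at 4 hour intervals after enrollment in the study", with no minimum change, and "Wheezing, bronchospasm, angioedema requiring rescue medications". The text does not say whether this list or the physician's discretion triggers the code break.

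**Timing.** Section 10, item 3: "Thirty minutes after enrollment, eligible subjects will be randomized into one of two arms". Section 10(f): "For subjects who receive t-PA, NAC or placebo infusion will be started 24 hours after the conclusion of the t-PA infusion".

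**Outcome rating.** For the day-30 and day-90 visits, Section 10 states: "A representative from the neurology department will perform the examination, blinded from the previous scoring and treatment". Section 10(f) names the follow-up examiner as a neurology resident. On inpatient care it says: "All subjects would then be admitted to the Neurology Service". Follow-up visits are standard of care, and the study team takes the results from the medical record.

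**The concern.** The primary endpoint is the NIHSS at 90 days, which a clinician scores. Two routes to bias open once a treating physician knows the arm.

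- **Co-treatment.** The physician may manage the subject differently by arm. NIHSS worsening is itself a listed serious event, so the subjects whose arm is revealed may be those doing badly early. Loss of blinding would then be related to outcome rather than occurring at random.
- **Scoring.** Blinding of the rater is a stated rule, but the plan does not say how it survives a code break. A resident who treated the subject, or who reads a note recording the assignment, could be the examiner at day 90. Nothing in the text prevents this.

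The enrollment-based clock adds an oddity. A t-PA subject may be randomized well before any study drug is given, so an early decline could reveal the assignment before dosing. At that point it cannot help to manage a reaction to the study drug.

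**Working it through.** The plan gives no expected rate of serious events, code breaks or leakage, so there is no planned figure to reproduce. The check is mainly textual, with one illustration.

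**Text, side by side**

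1. Is unblinding conditional on need? No. The sentence in Section 10(j) contains one discretion, over what is serious.
2. Can it depend on early outcome? Yes, if the fixed list is the trigger, because any NIHSS worsening qualifies.
3. Do other passages close the gap? The drug labels in Section 18 mask nurses, physicians and patients at the outset only. Section 10(i) covers access to stored study data. The physician not associated with the investigation, mentioned for adverse-event returns to the emergency department, does not rate the endpoint. None of these deals with the period after a code break.

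**Checks before dosing.** For a t-PA subject enrolled by the end of the t-PA infusion, the fixed list counts worsening from enrollment at 4-hour intervals, and study drug starts 24 hours after t-PA ends: 24 / 4 = 6 checks before any study drug. This counts opportunities; it does not estimate code breaks.

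**Illustration of scoring bias**

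Inputs from the protocol:

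- 117 subjects, 25% loss, SD 7.4, design difference 4.0 and one-sided alpha 0.05 (Section 10(b))
- wheeze and bronchospasm 7.1% (Section 11)

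Assumptions:

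- the 7.1% applies to the NAC arm
- every such case is disclosed to the rater
- each of these is scored 1 or 2 points too favourably
- placebo scores are unaffected

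Steps:

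- Enrolled per arm: 117 / 2 = 58.5. With a day-90 score: 117 × 0.75 / 2 = 43.9, taken as 44.
- Affected NAC subjects: 0.071 × 58.5 = 4.2 enrolled; 0.071 × 44 = 3.1 with a day-90 score.
- Standard error of the difference: 7.4 × √(2/44) = 1.578.
- Bias b = 0.071 × shift.
- One-sided type I error = 1 − Φ(1.645 − b/1.578).

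| Shift per affected subject | Bias b | Share of 4.0 | Type I error |
|---|---|---|---|
| 1 point | 0.071 | 1.8% | 5.5% |
| 2 points | 0.142 | 3.6% | 6.0% |

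With the plan's 47 per arm, the standard error is 7.4 × √(2/47) = 1.527 and the error rates are again 5.5% and 6.0%. A rank-sum simulation (normal data, 44 per arm, 100,000 trials) gave about 5% with no shift, 5.4% with 1 point and 6.0% with 2 points.

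This covers one reaction category and is not an upper bound. The 7.1% is also not a serious-event rate, since the fixed list counts these reactions only when rescue medication is needed. NIHSS worsening has no rate in the documents, and the co-treatment effect cannot be sized.

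**The case against.** The best case for the plan is that automatic disclosure is a deliberate trade of blinding for safety, and that it contradicts nothing else in the protocol. Rater blinding is already required. Because the examiner must also be blind to previous scoring, a resident who knows the in-hospital NIHSS scores is arguably ruled out. The unblinded physician may be in Emergency Medicine rather than Neurology. The pre-dosing scenario needs several conditions at once, and the disclosure sentence sits among text about infusion reactions. The illustrated bias is small, and no passage names a co-treatment that would differ by arm. Code-break handling might be set out in attachments such as the data collection sheets or in the pharmacy's randomization log.

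Much of this limits the size of the point, and it is accepted to that extent. The magnitude is unknown and the one calculable route is modest. The pre-dosing case is a possibility only. The absence of safeguards is claimed only for the text reviewed. It is also fair that the documents do not give resident numbers or pharmacist cover, so the staffing cost is a judgement.

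The central fact remains: disclosure is tied to seriousness and not to need, and the list of serious events reaches into the primary endpoint's scale. Release on the physician's own statement of need still gives that physician the assignment when care calls for it. This is a blinding procedure and changes no treatment rule.

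**Conclusion.** The concern holds. The plan unblinds the treating physician for every event classed as serious, without a need-for-care condition, under two unreconciled definitions, one of which includes any NIHSS worsening. The requirement for a blinded rater stands, but the text provides no means of keeping it after a code break.

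The effect on the result cannot be derived from the documents. Scoring bias is nil if nothing leaks. In the illustration it stays within 3.6% of the design difference, but that figure leaves out NIHSS worsening and co-treatment. The point should be fixed because the remedy is cheap and the loss of blinding can follow outcome. There is no showing that the bias is large. Confidence is medium.

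**What to change.** Amend the unblinding sentence in Section 10(j) and add a short procedure:

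1. The ED pharmacist releases the assignment promptly to the treating physician, or to any physician then caring for the subject, whenever that physician states that it is needed for care, and not otherwise. The medical monitor's receipt of the assignment, all stop orders and all safety reporting stay as they are.
2. Log each unblinding with date, reason and recipient.
3. Tell recipients not to pass the assignment to outcome raters, and not to enter it in notes the rater will read unless care requires it.
4. State that the day-30 and day-90 rater did not treat that subject and has not been told the assignment. Choose the rater from existing neurology residents.
5. Report the number of unblinded subjects by arm, and keep them in the primary analysis.
6. Reconcile the two definitions of a serious event in Section 10(j) and say which one triggers unblinding. The content is for the investigator to decide.

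**Cost.** Protocol wording, a pharmacist's log and some scheduling of raters in routine clinics. No new visits are needed, and no new staff are expected. The downside is one extra step before the treating physician learns the assignment.
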